10. DATA COLLECTION AND QUALITY ASSURANCE

10.1 Data Collection Forms

Study data will be collected at all clinical sites on paper CRFs identifiable by subject ID number. The electronic CRFs in OnCore are the official study documents. Local CRCs will enter data for their site (Mt. Sinai CRC will enter Mt. Sinai data, BCM CRC will enter BCM data) into OnCore. The CRCs will enter data on both paper and OnCore. CRF scans will be stored electronically in BCM-approved platform Box.

10.2 Data Management

Data will be stored securely at the Coordinating Center. Data and safety monitoring will be performed by the study statistician and external research coordinator (BCM Global Health). Data will be entered into the web application by authorized research personnel via secure HTTPS connections. De-identified data will be shared with the Co-investigators at Baylor, Mount Sinai, UC San Francisco, Medical University of South Carolina, and Rice University.

Only deidentified images (microscopic images) will be analyzed at Rice University, by the bioengineers who developed the devices and are collaborating on the project. The Rice team will not be responsible for other data analyses, interim/final or DRC report. The device being used in this study (the HRME) is manufactured in [name] lab at Rice University. The images collected from the clinical trial are used to build software that will work to automatically analyze data. While images are de-identified, some PHI will be transmitted (Date of Service only). A data use agreement will be issued stating this.

De-identified histopathologic slides will be shared with and read by a consensus pathologist at UCSF. All histopathologic slides and optical images will be labeled with the subjects study ID number and will be presented to the pathologist who will read them in a blinded fashion. The subjects' clinical research forms with the associated optical biopsy read(s) are similarly labeled with the subjects study ID number. There is no PHI shared with the slides. Material transfer agreements between BCM-UCSF & Mt. Sinai-UCSF and will be issued.

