6.2.3 Blinding

NA

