10.3.3 Metrics

Device qualification: Each mHRME and smart ring camera will undergo full quality control at the manufacturing facility prior to clinical use. Metrics to be evaluated include: illumination power & uniformity, spatial resolution, camera response, signal/noise ratio, accuracy of N/C area ratio and mean feature area as measured from standardized test targets. Illumination uniformity and camera response will be measured using a high-resolution imaging standard (e.g., 1951 USAF Hi-Resolution Target, Edmund Optics). Accuracy of N/C area ratio and mean feature area measurements will be evaluated using a test standard with a uniform standardized spatial pattern (e.g., 2285-26N image analysis standard slide, Ted Pella, Inc, or equivalent). Performance metrics will be required to be within 10% of target values prior to distribution to clinical sites.

Site performance: Initial visits to both sites will ensure proper training on the optimized mHRME, as well as allow for provider feedback on the modifications. Annual visits to the New York sites and weekly review of ALL video images from every patient accrued in the pilot trial provides assurance that the devices are performing consistently and uniformly. To insure further uniform performance, imaging test standards and training (described above) will be provided to technical personnel. Site technicians will be trained in device use, disinfection/sterilization, realignment and basic repairs; spare parts (LED modules, probes, cameras) will be available at all sites. Devices that cannot be repaired will be returned to Rice or Baylor for repair. An additional trip will be made at study initiation to ensure that the enhanced mHRME systems and image-assist software are standardized and functioning and at least annually thereafter.

The gold standard histologic diagnosis will be based on a consensus pathology review. After the result for the local pathologist is documented, the slides will be reviewed by another pathologist (who is blinded to the original review). If the two reads differ, then the histopathology slide will be adjudicated by a third pathologist. The final read will ensure consensus by 2 pathologists.

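### Section 10.2 passes optical images as well as slides to the consensus pathologist under an undefined blind, so review bias toward mHRME in the primary SN and SP is not excluded

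*Combined protocol and SAP*

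**What the plan says.** Section 9.6 makes histopathology the gold standard for the primary outcome (SN, SP, PPV and NPV of mHRME). Four places bear on how that histology is read.

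- Section 10.2 first names slides alone: "De-identified histopathologic slides will be shared with and read by a consensus pathologist at UCSF". Its next sentence widens this: "All histopathologic slides and optical images will be labeled with the subjects study ID number and will be presented to the pathologist". With its closing words, the sentence says that these items "will be presented to the pathologist who will read them in a blinded fashion". The object of the blind is not given.
- Section 10.2 then says that the "clinical research forms with the associated optical biopsy read(s) are similarly labeled with the subjects study ID number". It does not say that these forms go to any pathologist.
- Section 10.3.3 says that, once the local result is documented, "the slides will be reviewed by another pathologist (who is blinded to the original review". A third pathologist adjudicates if the two reads differ, and the final label needs two pathologists to agree.
- Section 6.2.3, the section on blinding, reads NA.

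**The concern.** In an accuracy study the reference read should be made without knowledge of the index test. Taken literally, section 10.2 gives a reference-standard reader the index-test image, linkable by study ID to the slide being graded. These images would mean something to a pathologist: section 2.1 says they show nuclear size and pleomorphism, and section 5.1 calls nuclear change the most important pathologic marker of squamous intraepithelial neoplasia. On a borderline slide, such as one near the AIN 2 threshold, the image could tip the grade.

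Any such pull makes histology agree with mHRME for a reason unrelated to the device's accuracy. It raises SN and SP together, and a larger sample does not reduce it.

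**Working it through.** **Text check.** There is no planned figure to reproduce, so the first step is to list what each reader is said to be masked to.

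| Reader | Masking stated | Masked to mHRME image, score or read? |
|---|---|---|
| Local pathologist (Appendix 1: diagnosis taken from Epic) | none | not stated |
| Second or consensus pathologist (10.2, 10.3.3) | blinded, object given only as the original review | not stated |
| Third, adjudicating pathologist (10.3.3) | none | not stated |

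The opposite direction is protected. In Appendix 1 the clinician's mHRME read and the image score are recorded before the biopsy is taken, so those real-time reads cannot be influenced by histology. Nothing equivalent protects histology from mHRME.

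No planned analysis needs a pathologist to see the images. Section 9.1 concerns physician- and algorithm-guided reads, and section 10.2 places image analysis at Rice University.

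**Illustration of size.** Inputs from the documents: preliminary SN 93% and SP 87% (section 2.1); HSIL prevalence 30% (section 9.2), applied here per biopsy site. Assumed input: *f*, the share of discordant final labels moved to agree with mHRME. The documents give no value for *f*.

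Per 100 sites:
- TP = 30 × 0.93 = 27.9; FN = 2.1
- TN = 70 × 0.87 = 60.9; FP = 9.1

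After relabelling: TP′ = TP + *f*·FP; FP′ = (1 − *f*)·FP; FN′ = (1 − *f*)·FN; TN′ = TN + *f*·FN.

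- *f* = 0: SN 93.0%, SP 87.0%.
- *f* = 10%: SN = 28.81 / (28.81 + 1.89) = 93.8%; SP = 61.11 / (61.11 + 8.19) = 88.2%. Shift +0.8 and +1.2 points.
- *f* = 25%: SN = 30.175 / (30.175 + 1.575) = 95.0%; SP = 61.425 / (61.425 + 6.825) = 90.0%. Shift +2.0 and +3.0 points.

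The starting accuracy matters. At 94% and 92%, the pilot values in the opening summary, *f* = 10% gives 94.7% and 92.8%, a shift below 1 point on each. At an assumed 80% and 80%, *f* = 10% gives 82.5% and 81.8%.

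For scale, the section 9.2 half-widths in the 80% and 85% rows run from 4.50 to 8.61 points. The illustrated shift is smaller than these, but it would not show in the confidence interval.

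**The case against.** The strongest reply is that the plan does state a blind, and that section 10.2 may be no more than a loosely worded labelling rule. Several parts of this stand.

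- A reader might infer that the consensus pathologist reads unblinded. The text does not support that: it says the read is blinded. The defect is a blind with no stated object.
- A reader might infer that slide and image are viewed side by side. Section 10.2 gives no order or session, and the sentence before names only slides.
- A shared study ID does not by itself unblind anyone. The recorded optical reads sit on the case report forms, which are not said to reach a pathologist.
- NA in 6.2.3 is weak evidence. It follows directly on a section saying there is no randomization and may refer only to participant or treatment blinding.
- One swayed reader does not set the label, because a second pathologist must agree. No section sends images to the local or third reader. The illustration applies *f* to the final label, so the share of individual reads swayed would have to be larger.
- A reader might quote an inflation of 2 to 5 points. That follows from assuming SN 85% and SP 80%, where *f* = 10% gives 86.9% and 81.8% and *f* = 25% gives 89.6% and 84.5%. Those starting values lie below the protocol's own preliminary figures.

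These points limit the claim but do not close the gap. The sentence does name optical images as presented to the pathologist, and a reader blinded to the local diagnosis alone would satisfy 10.3.3 while still seeing the mHRME image.

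**Conclusion.** The concern holds as a gap in the stated masking of the reference standard. The documents do not show that the histology is contaminated; they fail to rule it out, and section 10.2 as written permits it. The direction of any bias, if reads are drawn toward the image, is upward for both SN and SP.

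The size cannot be derived from the documents. About 1 to 3 points rests on three assumptions: 10% to 25% of discordant final labels shifted, true accuracy at the preliminary 93% and 87%, and 30% prevalence per site. The consensus rule would reduce it, and effective masking would make it zero. Because this touches the primary outcome and no planned analysis needs the images at the pathologist's desk, the text should be changed.

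**What to change.** - **Section 10.2:** send only histology slides to the consensus and adjudicating pathologists, under a per-biopsy slide code. The coordinating centre or the statistician holds the key from that code to the study ID. The key must exist, since the per-biopsy analysis in 9.6 depends on pairing each slide with its image.
- **Section 10.2 or 10.3.3:** state that these readers are masked to the mHRME image, the software score and the clinician's mHRME read, as well as to the original pathology review.
- **Section 10.2:** send optical images only to the image-analysis group.
- **Section 6.2.3:** replace NA with a cross-reference to this reader masking.

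The cost is the wording and the upkeep of a code key. No extra reader or procedure is needed. Routine local pathology on standard-of-care biopsies stays as it is. If the readers are already masked in practice, the amendment simply documents it.

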10.3 Quality Assurance

10.3.1 Training

All study staff have undergone their institutions' human subjects research and good clinical practice training. They will undergo OnCore training, training on CRF completion and data quality assurance. In addition, during the study start-up visit, all study staff will undergo training in HRME care, disinfection, and technical support.

10.3.3 Metrics

Device qualification: Each mHRME and smart ring camera will undergo full quality control at the manufacturing facility prior to clinical use. Metrics to be evaluated include: illumination power & uniformity, spatial resolution, camera response, signal/noise ratio, accuracy of N/C area ratio and mean feature area as measured from standardized test targets. Illumination uniformity and camera response will be measured using a high-resolution imaging standard (e.g., 1951 USAF Hi-Resolution Target, Edmund Optics). Accuracy of N/C area ratio and mean feature area measurements will be evaluated using a test standard with a uniform standardized spatial pattern (e.g., 2285-26N image analysis standard slide, Ted Pella, Inc, or equivalent). Performance metrics will be required to be within 10% of target values prior to distribution to clinical sites.

Site performance: Initial visits to both sites will ensure proper training on the optimized mHRME, as well as allow for provider feedback on the modifications. Annual visits to the New York sites and weekly review of ALL video images from every patient accrued in the pilot trial provides assurance that the devices are performing consistently and uniformly. To insure further uniform performance, imaging test standards and training (described above) will be provided to technical personnel. Site technicians will be trained in device use, disinfection/sterilization, realignment and basic repairs; spare parts (LED modules, probes, cameras) will be available at all sites. Devices that cannot be repaired will be returned to Rice or Baylor for repair. An additional trip will be made at study initiation to ensure that the enhanced mHRME systems and image-assist software are standardized and functioning and at least annually thereafter.

The gold standard histologic diagnosis will be based on a consensus pathology review. After the result for the local pathologist is documented, the slides will be reviewed by another pathologist (who is blinded to the original review). If the two reads differ, then the histopathology slide will be adjudicated by a third pathologist. The final read will ensure consensus by 2 pathologists.

10.3.4 Protocol Deviations

All protocol deviations will be reported to IRB and DRC in accordance with their policies.

In the event of an emergency, the sponsor and the reviewing IRB and DRC will be notified of any deviation from the protocol to protect the life or physical well-being of a subject. Such notice shall be given no later than 5 working days after the emergency occurred.

Otherwise, the quality monitoring processes by which deviations were identified, and process changes to prevent unintended variances will be reported to the IRB and DRC at continuing review.

10.3.5 Monitoring

All the study data (including Mt. Sinai and Houston data) will be monitored regularly by the Data Review Committee (DRC) of the Dan L Duncan Comprehensive Cancer Center, at a frequency of at least once per year, in accordance with the DLDCCC Data and Safety Monitoring Plan. The DRC will monitor the study for progress and enrollment, toxicities, adverse events, and soundness of data. Additionally, an independent research coordinator from BCM will monitor and review 25% of the data for accuracy

11. PARTICIPANT RIGHTS AND CONFIDENTIALITY

11.1 Institutional Review Board (IRB) Review

This project will comply with the National Institutes of Health (NIH) Policy on the Use of a Single Institutional Review Board (sIRB) of Record for Multi-Site Research. The proposed project will use the same protocol to conduct non-exempt human subjects research at four locations, and will not initiate human subjects research prior to obtaining sIRB approval.

sIRB – **Institutional Review Board for Baylor College of Medicine and Affiliated Hospitals (BCM IRB), Houston, TX.** All project sites (the Icahn School of Medicine at Mount Sinai, University of Florida, University of California, San Francisco and Rice University) have agreed to allow the BCM IRB to serve as the sIRB for this project. The BCM IRB will conduct the ethical review required by the Department of Health and Human Services regulations for the Protection of Human Subjects at 45 CFR Part 46 for all project sites. The BCM IRB also will serve as a Privacy Board to fulfill the requirements of the HIPAA Privacy Rule for use or disclosure of protected health information for research purposes.

The BCM IRB operates under the BCM Federal Wide Assurance No. 00000286, as well as those of hospitals and institutions affiliated with the College.

Should the project add any new sites after award, those sites also will rely on the BCM IRB as the sIRB of record.

Participating Sites – All participating sites will adhere to the sIRB Policy and will rely on BCM IRB to carry out the functions that are required for institutional compliance with IRB review set forth in the HHS regulations at 45 CFR 46. Participating sites will be responsible for meeting other regulatory obligations, such as obtaining informed consent, overseeing the implementation of the approved protocol, and reporting unanticipated problems and study progress to BCM IRB.

Participating sites will communicate relevant information necessary for the BCM IRB to consider local context issues and state/local regulatory requirements during its

deliberations. Participating sites are expected to rely on the BCM IRB to satisfy the regulatory requirements relevant to the ethical review. The investigators and local sites understand that although IRB ethical review at the local site level would be counter to the intent and goal of this policy, the policy does not prohibit any participating site from duplicating the sIRB. However, the PIs understand that if this approach is taken, NIH funds may not be used to pay for the cost of the duplicate review.

All participating sites will, prior to initiating the study, sign an authorization/reliance agreement that will clarify the roles and responsibilities of the BCM IRB and the participating sites. The BCM IRB will maintain records of the authorization/reliance agreements and of the communication plan.

Communications Between Participating Sites BCM IRB – BCM IRB will collaborate with the BCM PI to establish a mechanism for communication between BCM PI and the participating sites. The proposed plan is as follows:

- 1) The BCM uses the SMART IRB platform to initiate and establish authorization/reliance agreements and prior to any site initiating the research, each site will sign an authorization/reliance agreement that will clarify the roles and responsibilities of the BCM IRB and participating sites. These reliance agreements will be maintained at the BCM IRB office as well as with each participating site.
- 2) The BCM PI, with assistance from the BCM IRB office, will collect local context issues and federal/state/local regulatory requirements for each participating site.
- 3) The BCM PI will develop master study specific templates for Informed Consent Form (ICF), as well as HIPAA authorization, which will include local context for all participating sites and submit a single protocol to the BCM IRB that will be reviewed, approved, and used at all participating sites.
- 4) After BCM IRB reviews and grants final approval, the BCM PI will provide the participating sites with the IRB-approved versions of all study documents.
- 5) The BCM PI will be responsible for preparing and submitting IRB applications on behalf of all sites, including initial reviews, local amendments, personnel updates, local reportable events, and study wide information for continuing review.
- 6) The BCM PI will be responsible for communicating all IRB actions and determinations to all participating sites as well as maintaining the documentation of all required communications with participating sites under this plan.

11.2 Informed Consent Forms

The Baylor PI will develop master study specific templates for Informed Consent Form (ICF), as well as HIPAA authorization, which will include local context for all participating sites and submit a single protocol to the BCM IRB that will be reviewed, approved, and used at all participating sites. The BCM PI will be responsible for preparing and submitting IRB applications on behalf of all sites, including initial reviews, local amendments, personnel updates, local reportable events, and study wide information for continuing review.

All participating sites will adhere to the sIRB Policy and will rely on BCM IRB to carry out the functions that are required for institutional compliance with IRB review set forth in the HHS regulations at 45 CFR 46. Participating sites will be responsible for meeting other regulatory obligations, such as obtaining informed consent, overseeing the implementation of the approved protocol, and reporting unanticipated problems and study progress to BCM IRB.

11.3 Participant Confidentiality

Participation in research may involve loss of privacy. Research records will be handled as confidentially as possible within the law. All records linking patient identifiers with unique study identifiers will be coded and kept in password protected files, so that only the study investigators have access to them. All data and information will be stored in files that are stripped of identifiers. No individual identities will be used in any reports or publications resulting from this study. The subject records may be reviewed by the research staff, and the study site Institutional Review Board, the National Institutes of Health (NIH), the Office for Human Research Protections (OHRP), and their designees.

We plan to obtain a Certificate of Confidentiality from the National Institutes of Health. With this Certificate, the researchers cannot be forced to disclose information that may identify the subject, even by a court subpoena, in any federal, state, or local civil, criminal, administrative, legislative, or other proceedings. The researchers will use the Certificate to resist any demands for information that would identify the subject, except as explained below. The Certificate cannot be used to resist a demand for information from personnel of the United States Government that is used for auditing or evaluation of federally funded projects or for information that must be disclosed in order to meet the requirements of the federal Food and Drug Administration (FDA).

11.4 Study Discontinuation

The study may be discontinued at any time by the IRB, the DLDCCC DRC, the NIH, the OHRP, the FDA, or other government agencies as part of their duties to ensure that research participants are protected. The participant has the right to withdraw from the study at any time.

12. COMMITTEES

N/A

13. PUBLICATION OF RESEARCH FINDINGS

Publications will be reviewed by the co-PIs and the co-Is of the study

15. SUPPLEMENTS/APPENDICES

Appendix 1: Manual of Operations

MOP - HRME at Thomas Street Clinic

H-44616: THE EFFECTIVENESS OF HIGH RESOLUTION MICROENDOSCOPY (HRME) IN HIGH GRADE INTRAEPITHELIAL LESIONS (HSIL) DIAGNOSIS FOR PEOPLE LIVING WITH HIV

Supplies to take:

- Proflavine (dispensed from Investigational Pharmacy)
- Pen
- Staple remover
- Stapler
- Research charts (Consent Forms, CRF, Questionnaires, Proflavine Order form)
- Watch/phone

4 Weeks Prior to Clinic:

- 1. Patient is identified either by looking at clinic schedule or in clinic by Physician. Physician notifies CRC (via email or phone) to provide consent form for patient's review.
- 2. Physician discusses procedure with patient and answers questions. Physician adds note in Epic that procedure was discussed (using templates below). If patient is interested and agrees to enroll, use Epic Note Template #1 and continue to Step 3. If patient wants to keep consent form and further review, use Epic Note Template #2 and instruct patient not to sign consent. If patient is not interested, use Epic Note Template #3 so they are not approached again.

Epic Note Templates

#1: If patient wants to enroll

"I discussed study H-44616 with the patient, including study procedures. Patient was enrolled on [date]. Study procedure is being scheduled."

#2: If patient wants to further review

"I discussed study H-44616 with the patient, including study procedures. A copy of the consent form was given to the patient for his/her review, with instructions not to sign the consent until they returned to clinic. The patient can contact clinical research coordinator to follow-up regarding questions and interest in participating."

#3: If patient is not interested

"I discussed study H-44616 with the patient, including study procedures. Patient was not interested in study and should not be approached again."

3. The CRC should sign and date the consent form after the patient has signed. If a translator and foreign language consent form were used, the translator will sign and date on translator line. The original consent form(s) will remain in the research chart. Make two copies of the signed consent form(s). Place one copy of all languages used in the medical chart for scanning

into Epic by the nurse and give a copy/copies to the subject. The subject's copy should have CRC's contact info written on it (or business card) so the subject can contact our office with any questions or concerns.

- 4. Take the patient ID stickers from the medical chart. Place a sticker on each page of the consent form. If a foreign language consent form is used, place stickers on each page of both consent forms.
- 5. CRC completes pages 1-2 of the CRF and questionnaire packet at time of consent in English or in Spanish (HRME Sexual Behaviors and Sexual History for men and women, EQ-5D-5L).
- 6. Procedure is scheduled (by research scheduler).
- 7. CRC verifies the appointments have been scheduled by reviewing Epic and confirms with patient over the phone.
- 8. CRC registers patient in OnCore and assigns patient study ID based on OnCore ID.

7 Days Prior to Clinic:

- 9. CRC completes the Proflavine order form for study by providing, name, DOB, MRN, and study ID (or placing patient sticker with above information). CRC verifies patient allergies in Epic (Iodine, Proflavine).
- 10. Send the completed Proflavine order form to Investigational Drug Service to prepare the Proflavine batch. Place confirmation (email/fax confirmation) and original Proflavine order form in the research chart.
- 11. CRC will inform HRME operator of the date and time of HRME clinic, and the anticipated number of HRME study patients.

2 Days Prior to Clinic:

- 12. CRC will send reminder email to physician and HRME operator to remind them of clinic schedule.
- 13. CRC prepares research charts for n+1 (extra) patients scheduled for that clinic. Research charts should include the following: consent form (English, Spanish), CRF, questionnaires, and Proflavine order form. Research charts will be stored in CRC's locked office file cabinet.

Day of Clinic: CRC will coordinate with the physician's clinic staff to block off appropriate number of slots.

14. CRC arrives at clinic 30 minutes before scheduled clinic appointment to set up. CRC picks up Proflavine from Investigational Drug Service.

- 15. Once a patient is checked in, CRC leads them back to research office or procedure room to complete any unfinished questionnaires and baseline symptoms screen.
- 16. Complete pages 2-10 of the CRF with the subject, using the translation services if necessary. The baseline symptoms form should be completed the day of the procedure.
- 17. Record the Proflavine lot number and expiration date from the syringe packaging in CRF.
- 18. Give Proflavine to nurse in procedure room to administer during procedure and log into Epic.
- 19. During the procedure, complete the CRF (pages 11-20).
 - a. Record scope in time, HRA start time (page 12)
 - b. Record first abnormal area as Biopsy 1 (page 13)
 - i. Describe lesion, mark location, take anoscopy image
 - ii. Record clinician HRA read, plan (standard of care)
 - c. Go onto second abnormal area as Biopsy 2 (page 14)
 - i. Describe lesion, mark location, take anoscopy image
 - ii. Record clinician HRA read, plan (standard of care)
 - d. Repeat above steps for each abnormal area using extra biopsy pages if necessary
 - e. Record HRA end time. Apply Proflavine, insert HRME. Record HRME start time.
 - f. Proceed to first abnormal area (Biopsy 1)
 - i. Once feed is in focus, freeze HRME
 - ii. Record clinician read and plan based on HRME image
 - iii. Analyze image. Record image number and score.
 - iv. Ask clinician if they are happy with this image or if they would like to take another. Take as many images as needed, using extra biopsy pages if necessary
 - v. Select best image of site (most representative)
 - g. Go onto Biopsy 2.
 - i. Once feed is in focus, freeze HRME
 - ii. Record clinician read and plan based on HRME image
 - iii. Analyze image. Record image number and score.
 - iv. Ask clinician if they are happy with this image or if they would like to take another. Take as many images as needed, using extra biopsy pages if necessary
 - v. Select best image of site (most representative)
 - h. Repeat above steps for each Biopsy using extra biopsy pages if necessary
 - i. Record end HRME time. Remove HRME attachment and insert biopsy forceps. Record biopsy start time.
 - j. Proceed to Biopsy 1, biopsy area. Place sample in labeled specimen container. Record specimen label.
 - k. Repeat for each biopsy.

- 1. Record biopsy end time.
- m. Record scope out time.

Within 2 Days of the Clinic:

20. Within 2 days of the procedure, CRC calls the study participant and complete the Follow Up Symptoms form. Be sure to provide the study participant with CRC and PI phone number (business card/consent form) in case of any adverse events. Any adverse events or serious adverse events reported during the phone call should be reported to PI within 24 hours of being reported. If applicable, the CRC and PI will complete the Serious Adverse Event form. The PI will inform the local and IRB of record if needed within 5 days.

Within 30 Days of the Clinic:

- 21. Within 30 days of the procedure, CRC calls the study participant and complete the Follow Up Symptoms form. Be sure to provide the study participant with CRC and PI phone number (business card/consent form) in case of any adverse events. Any adverse events or serious adverse events reported during the phone call should be reported to PI within 24 hours of being reported. If applicable, the CRC and PI will complete the Serious Adverse Event form. The PI will inform the local and IRB of record if needed within 5 days.
- 22. CRC obtains the HRA procedure report, local pathology diagnosis from Epic. Place them in study participant's research chart. Record the local pathology diagnosis for each biopsy in CRF.
- 23. Request images from HRME operator.
- 24. CRC reviews chart, source documents, consent form, and Epic record for each local subject.
- 25. After completion of all study requirements, CRC and site PI will sign and date the Study Completion Form.
- 26. CRC scans the de-identified CRF and HRA procedure report, collects HRME images, and uploads into Box.
- 27. Paper copy of the original CRF and print out of pathology report, along with consent form and print out of HRA procedure report, are filed in CRC's office. Research charts should be stored in locked file cabinet when not in use. Secure workstation (Epic, computer, charts) if away from desk.
- 28. CRC will complete data entry in OnCore.
- 29. Data entered into OnCore will be monitored by Project Manager at Baylor College of Medicine including 100% of adverse events and ICFs and 25% of all charts at both sites.

30. The BCM IRB will annually review all adverse events. SAEs will be reported and reviewed within 5 days. Any event that is reportable to the BCM IRB will also be reported to the DLDCCC DRC and FDA in accordance with their policies.

Follow Up Evaluation:

At 1 year and 2 years post-enrollment, patients will be contacted via phone to assess rates of disease progression and recurrence. Patients will be contacted 3 times within 3 months of follow up time point. If they are unable to be reached, they will be designated "lost to follow up".

Adverse Event/Serious Adverse Event Definition

Serious adverse events will count as Grade 3 (Severe or Medically Significant, but not Immediately Life Threatening: Hospitalization or Prolongation of Hospitalization Indicated; Disabling; Limiting Self Care ADL), Grade 4 (Life-threatening consequences; urgent intervention indicated) or Grade 5 (Death related to AE).

Data Safety Monitoring

We will follow the Cancer Therapy Evaluation Program (CTEP) guidelines for reporting of adverse events. All expedited adverse event reports are required to be submitted to the local Institutional Review Board (IRB) of the reporting institution. Baylor College of Medicine has a standardized system for data and safety monitoring used by all investigators conducting NIH-funded research on patients. This includes a preliminary evaluation by the Dan L. Duncan Cancer Center (DLDCC) PRMC during the scientific review process, and an Institutional Review Board (IRB) review of serious and unexpected adverse events. Additionally, an independent research coordinator from BCM will monitor and review 25% of the data for accuracy , and 25% of all charts at both sites. 100% of adverse events will be monitored by the PI and study team. On site audits will be conducted every 6 months. [name] (Research Coordinator) and [name] will handle all reporting to the FDA for IND for proflavine.

All the study data (including Mt. Sinai and Houston data) will be monitored regularly by the DLDCCC DRC Data Review Committee (DRC) of the Dan L Duncan Comprehensive Cancer Center, at a frequency of at least once per year, in accordance with the DLDCCC Data and Safety Monitoring Plan. The DRC will monitor the study for progress and enrollment, toxicities, adverse events, and soundness of data. Each site will plan to have weekly meetings. At each weekly meeting, the Project Coordinator will provide the following information: number of participants entering the study, status with respect to meeting recruitment targets, percentage of patients assessed who enter the study, number of drop-outs, reasons for drop-out, percentage of patients at each stage of the project, and percentage of assessments completed at each assessment point. Information about any adverse events (including IRB reporting of short- and long-term remedies) also will be presented. By examining this information, the data and safety monitoring team will keep abreast of critical issues regarding recruitment and data integrity. Study staff also will notify at least one supervisor immediately if at any point a patient shows the need for urgent treatment (e.g. diagnosis of cancer). A written report containing the current status the trial monitored while the IND is active, and when appropriate, any toxicity and outcome data, are sent to DRC members at a frequency specified by the DRC Charter, which is usually annually.

Helpful phone numbers: Harris Health Translation Services Thomas Street Translator: [contact]

Investigational Drug Service (IDS): [name], Pharmacist

Email: [contact] [contact] Office: [contact] [contact]

HRME Operator: [name]

Email: [contact] [contact]

Consent forms - who signs, who gets a copy?

Using translated short form:

	Short form	English long form
Subject	Signs, gets a copy	Gets a copy
Witness/translator	Signs	Signs
PI/designee	-	Signs

Using Spanish long form:

	Spanish long form	English long form
Subject	Signs, gets a copy	Gets a copy
Witness/translator	Signs	Signs
PI/designee	Signs	Signs

**If designee is fluent in Spanish, he/she can sign as translator but must have a witness fluent in both languages to sign as the witness

